**Note: Do not include a list of citations in this section. Please limit this section to no more than 300 words.**

Alcoholism is the third leading cause of preventable death in the US, accounting for 80,000 deaths annually. Almost 18 million US adults have alcohol use disorder (AUD); however, approved medications for the treatment of AUD has shown limited effectiveness.

Zonisamide (ZON), a broad spectrum anticonvulsant, has proven to be more effective than a placebo in reducing alcohol intake in individuals with alcohol dependence. ZON’s mechanism of action seems to be quite distinct from currently approved anti-alcoholism medications, which holds promise for treatment of individuals who are not responsive to conventional medications.

However, much remains unknown about ZON's therapeutic mechanisms and ZON's efficacy in treating patients with a diagnosis of AUD.

To fill in these gaps, we will conduct a double-blind randomized controlled study that assesses ZON's treatment mechanisms and effectiveness in reducing alcohol consumption in patients with AUD. Participants will be randomized to one of two conditions: 1) treatment with ZON and a computerized alcohol reduction and medication compliance program called *Take Control* (TC); 2) treatment with a placebo (PLC) and TC. To understand the neurobiology behind ZON's potential therapeutic effects on AUD, fMRI will be acquired at baseline (pre-treatment) and near the end of study treatment and used to compare the brain activity of the ZON+TC versus PLC+TC group while they perform an alcohol and emotional-word Stroop task, as well as an alcohol related cues task.

Compared to the PLC+TC group, we hypothesize that the ZON+TC group will: 1) have significantly greater reductions in alcohol consumption by the end of a 12-week treatment period; 2) show enhanced midbrain-frontal connectivity while performing the Stroop task during an fMRI procedure; and 3) decreased limbic and prefrontal activity during an alcohol cues task.

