#### Overview

Potential participants will complete a telephone and an in-clinic screening to determine eligibility for this study. Eligible participants will be randomized to receive one of two treatment conditions: 1) Zonisamide plus *Take Control* (a computerized alcohol reduction and medication compliance program developed by the National Institute on Alcohol Abuse and Alcoholism (NIAAA)); 2) a placebo plus *Take Control*. For both conditions, participants will receive 12 treatment sessions. Participants will receive medication at each session, and they should have two weeks worth of medication on hand at any given time. Participants will take the medication as prescribed at home. The first 11 treatment sessions will include *Take Control*. The 12 treatment sessions will be followed by two drug dose taper sessions, and a follow up phone interview immediately following the final session.

Participants will also undergo two scans of less than 2 hours duration, one before they begin study sessions and the second near the end of the study (12th study week and before the medication taper). At the in-clinic screening session, participants will receive a “MRI Information for Research Participants” handout that answers some commonly asked questions about MRI and tells participants what they can expect while undergoing an MRI scan. Both scans will be conducted at BU CILSE. Participants will be screened before each scan session for pregnancy (urine sample, women of childbearing potential only), recent smoking or alcohol use (breathalyzers), and illicit substance use (urine sample). Participants will be asked to complete the Alcohol Urge Questionnaire (AUQ) before and after the scan. Participants will also be asked to complete item #8 from the AUQ before and after the Alcohol Cues Task. Eligible participants will complete a 1-hour 3 Tesla MRI scan involving structural imaging (MRI) and functional imaging (fMRI). The fMRI scans include a resting-state scan (no task involved) a cognitive (Stroop) task, and an alcohol cue reactivity task. The latter two scans involve presentation of visual images to participants while they are in the scanner. No contrast agent or invasive procedures are used. Only personnel trained in working in high magnetic field environments will work on this project. Imaging data will be analyzed on secure networks using only encrypted files. All data obtained will be coded to protect participant privacy and confidentiality.

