#### V. Neuropsychological Assessments

Neuropsychological function will be assessed using Hopkins Verbal Learning Test (HVLT), Wechsler Adult Intelligence Scale-IV's (WAIS-IV) Letter-Number Sequencing and Digit Span, WMS-IV Symbol Span, Delis-Kaplan Executive Function System (D-

KEFS) Letter Fluency and the Wide Range Achievement Test-IV (WRAT-IV). Impulsivity will be evaluated using the CPT and the Go/No Go task. Risk taking behaviors will be measured with the Balloon Analog Risk Task and the Rogers Risk task during weeks 1 and 12. Functional and structural images will be acquired during the Stroop test and Alcohol Cues task during fMRI imaging sessions, which will be administered at study weeks 1 and 12.

- A. Hopkins Verbal Learning Test-Revised (HVLT-R; Brandt & Benedict, 2001)** – The HVLT-R is a brief assessment of verbal learning and memory (recognition and recall) for individuals 16 years and older. The HVLT-R requires recall of a series of 12 words over three learning trials, free recall after a delay, and a recognition trial. The assessment takes approximately 5-10 minutes, with a 25-minute delay, to complete.
- B. Wide Range Achievement Test-IV (WRAT-IV; Wilkinson, G. S., & Robertson, G. J., 2006)** – The WRAT-IV is a norm-referenced test that measures the basic academic skills of word reading, sentence comprehension, spelling, and math computation.
- C. Symbol Span: Wechsler Memory Scale (WMS-IV; Wechsler, 2009)** – The WMS-IV is a neuropsychological test designed to measure the various memory functions of a person. The measure includes 7 subsets and A person's performance is reported as five Index Scores: Auditory Memory, Visual Memory, Visual Working Memory, Immediate Memory, and Delayed Memory.
- D. Delis-Kaplan Executive Function System-Letter Fluency (D-KEFS; Delis, Kaplan, & Kramer, 2001)** – D-KEFS is a neuropsychological test used to measure a variety of verbal and nonverbal executive functions (reasoning, planning, problem solving, etc.) for both children and adults (ages 8-89 years).
- E. Digit Span and Letter Number Sequencing: Wechsler Adult Intelligence Scale (WAIS-IV; Weschler, 2008)** - The WAIS-IV is a neurological test developed to assess cognitive ability in adults. This instruments aids in examining the relationship between intellectual function and memory. The test includes 11 subtests of various formats. Approximately 60 to 90 minutes is required for completion.

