#### Data Analysis

1. Demonstrate that ZON will attenuate changes resulting from performance on alcohol-word and negative-word Stroop tasks in the activity of frontal-parietal and midbrain regions and the connectivity to networks associated with these regions in AUD subjects. Our working hypothesis is that midbrain activity will be lower in ZON treated subjects than in placebo subjects following performance on alcohol and negative emotion Stroop task, which will occur in association with enhanced mid-brain-frontal connectivity and increased synchrony.

Fixed effects models will be used to analyze data for brain activation in regions of interest, with treatment group as a between group factor and Stroop task type and order of stimuli presentation will be within subject factors. Regions of interest will include parahippocampal gyri, midbrain substantia nigra and red nucleus, dorso-lateral prefrontal cortex, and cerebellum.

Connectivity will be assessed using the Free Surfer analysis described below. Seeds will be used for the dorsolateral prefrontal cortex and the midbrain (substantia nigra) following Muller-Oehring et al. (2013).

2. Demonstrate that ZON administration attenuates the enhanced regional brain activity and craving- induced by exposure to alcohol related cues in AUD subjects. Our hypothesis is that exposure to alcohol-related cues will increase brain activity in select limbic and prefrontal areas to a lesser degree in ZON as compared to placebo treated AUD subjects.

Fixed effects models will be used to analyze data for brain activation in regions of interest, with treatment group as a between group factor and stimulus type and order of stimuli presentation was within subject factors. Regions of interest, based on the meta-analysis of Schacht et al. (2013), will include the ventral striatum, medial prefrontal cortex, and the anterior cingulate cortex.

3. Demonstrate that the ZON induced changes in brain activity are predictive of reduced ethanol consumption.

Logistic regression analysis will be used to evaluate zonisamide-induced decreases in the BOLD response in the ventral striatum and the medial prefrontal cortex as predictors of complete abstinence or reduction to safe drinking levels (defined as consumption of no more than more than 2 standard drinks per day) during study weeks 10 to 12.

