Resting state DICOM scans will be converted to Nifti files with MRIcron's *dcm2nii* in order to be processed in The Functional Connectivity Toolbox 2014 (CONN). CONN is a Matlab-based cross-platform software that will be used to compute, analyze the functional connectivity of fMRI (Whitfield-Grabrielli and Nieto-Castanon, 2012). The CONN toolbox uses Matlab version 2012 and SPM8 to process the resting-state fMRI scans into ROI-to-ROI connectivity matrices, test hypotheses and visualize data (Whitfield-Grabrielli and Nieto-Castanon, 2012). CONN uses a seed-driven RSFC analysis strategy, where the pearson's correlation coefficient is calculated between the seed time course and the time course of all other voxels (Whitfield-Grabrielli and Nieto-Castanon, 2012). The correlation coefficients are converted to normally distributed scores using Fisher's transformation to allow for second-level General Linear Model analysis (Whitfield-Grabrielli and Nieto-Castanon, 2012). The correlation maps depend on the specific location of the seed so that functionally and anatomically heterogenous ROI are dissociated in order to delineate functional anatomy in the brain by sharp transitions in correlation patterns that signal functional boundaries across the cortex (Whitfield-Grabrielli and Nieto-Castanon, 2012).

The subject's processed MPRAGE scans are imported into CONN, and used alongside the resting state scans. CONN uses CompCor strategy for spatial and temporal preprocessing to

define and remove confounds in the BOLD signal to prevent the impact of physiological noise factors and motion in the data (Behzadi et al., 2007). The CompCor strategy is unique because it is more flexible in its characterization of noise (Behzadi et al., 2007). CompCor models the influence of noise as a voxel-specific linear combination of multiple empirically estimated noise sources, which are estimated from the variability in the BOLD responses within noise ROIs (Behzadi et al., 2007). This is important for the removal of fMRI noise because cardiac and respiratory effects do not have a common spatial distribution in their effects. The removal of this richer characterization of the range of voxel-specific noise effects and additional movement along with temporal filtering and windowing the BOLD signal at each voxel protects against confounds in RS-FC without introducing artifactual biases in connectivity measures.

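### The connectivity hypothesis concerns the Stroop task, but the only connectivity analysis specified uses resting-state scans

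*Combined protocol and SAP*

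**What the plan says.** **The hypothesis.** Section G (Study Summary) gives three hypotheses. The second is that the zonisamide group will "show enhanced midbrain-frontal connectivity while performing the Stroop task during an fMRI procedure". In Section L, item 1 of Data Analysis (Aim 1 below) concerns changes that result from the Stroop tasks, in both regional activity and connectivity. Its working hypothesis is lower midbrain activity after the Stroop, "which will occur in association with enhanced mid-brain-frontal connectivity and increased synchrony".

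**The method it is sent to.** Aim 1 writes a treatment-group model for activation. For connectivity it gives a pointer: "Connectivity will be assessed using the Free Surfer analysis described below". It adds that seeds will be placed in the dorsolateral prefrontal cortex and the substantia nigra, following a cited 2013 study.

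**What that section analyses.** FreeSurfer Analysis first describes structural processing. It then describes CONN, which is used "to process the resting-state fMRI scans into ROI-to-ROI connectivity matrices, test hypotheses and visualize data". The processed structural "scans are imported into CONN, and used alongside the resting state scans". The estimator is a seed-based resting-state correlation, Fisher-transformed and passed to a group-level linear model. The section ends with 99 regions used as seeds.

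**The scans.** The Overview of Section L keeps the scans apart: "The fMRI scans include a resting-state scan (no task involved) a cognitive (Stroop) task, and an alcohol cue reactivity task". The Neuropsychological Assessments section says images are "acquired during the Stroop test and Alcohol Cues task during fMRI imaging sessions, which will be administered at study weeks 1 and 12".

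**The concern.** The hypothesis and the analysis assigned to it refer to different data. The hypothesis is about how midbrain and frontal regions work together while a person does the Stroop. The analysis measures how regions correlate when the person is doing nothing.

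A difference between arms at rest would be a legitimate finding about zonisamide. It would not show that connectivity changed during the Stroop, or because of it. Followed as written, the plan would report that resting-state difference as the Aim 1 connectivity result. If the gap is noticed only after unblinding, the choice of scan, seeds and contrast would have to be made with the treatment allocation known.

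**Working it through.** No sample size, power or alpha figure in the plan depends on this point. The only imaging figure under Power Analysis is for ventral striatum activation. The check is therefore a reading of the sections side by side.

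1. **Match each Section G hypothesis to an analysis in Section L.**
   - Hypothesis 1 (drinking): item 4 of Data Analysis, a repeated-measures mixed model on the timeline follow-back measures. Matched.
   - Hypothesis 2 (midbrain-frontal connectivity during the Stroop): Aim 1, which points to FreeSurfer Analysis. Checked in steps 2 to 4.
   - Hypothesis 3 (limbic and prefrontal activity during alcohol cues): item 2, an activation model in named regions. Matched.

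2. **List the inputs in FreeSurfer Analysis.** The FreeSurfer pipeline steps (motion correction, skull stripping, segmentation, surface generation) are structural. In the CONN part, the files converted for input are resting-state files, the scans turned into connectivity matrices are resting-state scans, and the structural images are paired with resting-state scans. The correlation method is itself described as a resting-state one. Stroop runs are named nowhere in the section.

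3. **Ask whether the resting-state scan could count as a Stroop scan.** The Overview says it involves no task and lists it separately from the Stroop scan. It cannot represent connectivity during the Stroop.

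4. **Look for a Stroop connectivity analysis elsewhere.** Two places come close.
   - The Analysis part of Imaging Acquisition and Processing requires task-against-control contrasts and sets a Z threshold of 2.3 with cluster p of 0.05. It does so within the FSL model of the BOLD response, which is the activation analysis. It defines no connectivity measure.
   - Aim 1 names two seeds but not the scan they apply to, and the section it points to is resting-state only.
   - No task-modulated or condition-specific connectivity method is described in any section, and no rule links resting-state connectivity to the Stroop hypothesis.

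5. **Result.** Specified connectivity steps that use Stroop data: 0. Section G hypotheses with a matching analysis: 2 of 3. Hypotheses without one: 3 − 2 = 1.

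6. **Are the data for a repair already planned?** Yes. Stroop imaging is scheduled at weeks 1 and 12, so each participant who completes both sessions has a Stroop scan before treatment and one near its end.

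**The case against.** **Section G is a lay summary with a word limit, and Aim 1 is looser.** This is true. Only Section G says the connectivity is measured during the task. Aim 1 leads with midbrain activity and says the connectivity change occurs in association with it. A reader might go further and infer that Aim 1 as a whole has no analysis. The documents do not support that, because the activation part has a stated model. The connectivity part of Aim 1 is still framed as a consequence of the Stroop, so the looser wording narrows the gap without closing it.

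**Aim 1 speaks of effects following the Stroop, so a resting scan after the task might serve.** The documents do not state the order of the scans, so this reading can be neither confirmed nor excluded. A reader might take the order in which the Overview names the scans as the order of acquisition; a list does not establish that. In any case a post-task resting scan would not answer the Section G wording.

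**The FreeSurfer section says that all of a participant's MRI scans are processed, and it mentions functional data.** That is a general statement of scope. The steps that follow yield no Stroop connectivity measure.

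**Two seeds and 99 regions are not in conflict.** This stands. A 99-region matrix could include the two seeds, so the two descriptions can coexist. What is missing is a statement of which analysis tests the Aim 1 hypothesis.

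**The cited 2013 study may define more.** It may, and it was not available here. It is cited for the seeds, and that does not change which scans the CONN text processes.

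**Conclusion.** The mismatch is real and should be fixed. As written, no specified connectivity step uses Stroop data, and one of the three Section G hypotheses has no analysis that answers it. The Aim 1 activation analysis and the item 4 drinking analysis are unaffected.

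The conclusion rests on the text of the combined protocol and SAP alone. It assumes that no separate imaging analysis plan supplies a Stroop connectivity model. The Covid-19 Protocols paragraph moves study sessions to remote contact and does not say whether scanning continued, so the number of usable Stroop scan pairs is unknown.

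One related item is a minor check, not part of this conclusion. Section G and Aim 1 refer to emotional or negative words, while the description of the Stroop task under Neuropsychological Assessments names alcohol, colour and neutral words. A reader might infer that negative words were never shown. The description gives only examples, and a stimulus list may exist outside this file, so the documents show a discrepancy and no more.

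**What to change.** Before any unblinded imaging analysis, take one of two routes.

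- **Route A: test the hypothesis as stated.** Specify the Aim 1 connectivity test on the Stroop runs scheduled for weeks 1 and 12. Make it a zonisamide versus placebo comparison of connectivity between the dorsolateral prefrontal and substantia nigra seeds, with the week 1 value in the model, and write out that model and its threshold. Add a word-type contrast only if the presentation timing supports it. The task description can be read as every block mixing word types, so check the timing first. Label the resting-state 99-region analysis secondary.
- **Route B: restate the hypothesis.** Reword Section G and Aim 1 as resting-state connectivity, and claim no Stroop-related effect from it.

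Separately, check the stimulus list actually used, then either correct the task description or remove the negative and emotional word references from Section G and Aim 1. The task itself should not be changed: the Covid-19 paragraph shows the trial is under way.

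Route A costs some analyst time to set up a task-based connectivity model and needs no additional scans. Route B costs only wording but leaves Aim 1 narrower.

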### Randomization

Participants who continue to be eligible for the study following the in-clinic screening will be randomized to one of two treatment conditions: 1) Zonisimaide and *Take Control* (TC) computerized program; 2) a placebo and TC. An adaptive randomization will be used, where gender, heavy drinking, handedness, and smoking status will be variable levels.

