### Study Sessions

All participants will be required to have a BAC of 0.02% or less to complete study sessions. Following screening, subjects will receive either ZON or drug placebo (and TC) for 12 weeks, followed by a 2 week taper off medication. Most weekly study sessions will be approximately 45-60 minutes in duration. Session 1 will be approximately 3 hours, while session 12 will be approximately 2 hours in duration. Follow-up data will be collected at the end of the drug taper (week 14) and then again two weeks later (at study week 16). We will allow up to four weeks for completion of this week 16 follow-up phone assessment. Therefore, participants will have a 20-

week window to complete all study procedures before their participation is considered complete. Assessments that will be obtained during the course of the study are shown in Table 1.

We will ask participants to schedule a standing appointment for each week of the 14-week study, with each appointment scheduled 7 days apart. However, we will allow participants to reschedule an appointment between 7-10 days after their previous session if necessary. The length of time until the subsequent session would then be modified in an attempt to re-establish the original schedule. If a session is scheduled beyond this 7-10 day window (i.e., days 11-14), the session will still be conducted but will be considered the next session. The prior session will be considered “missed.” Participants who miss two consecutive sessions during any 14-day period will be tapered off the study medication and withdrawn from the trial for safety reasons. Participants who are withdrawn will be asked to return weekly to complete the medication taper.

*Interventions:*

Medication treatment (Zonisamide vs. placebo) and Take Control will be administered using a double-blind procedure to subjects during scheduled visits over a period of 14 weeks.

I. Zonisamide (ZON):

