4. Replicate the finding that ZON will reduce alcohol consumption in AUD subjects. Our working hypothesis is that the drinks consumed per day and percent days drinking will be significantly lower in AUD subjects receiving ZON than in those treated with placebo.

Drinking measures derived from the TLFB data will include the percent days drinking, the number of drinks consumed per day, and the percent days heavy drinking. Heavy drinking will be defined as 4 or more drinks per day for women and 5 or more drinks per day for men.

Alcohol consumption measures will be analyzed using repeated measures mixed models analysis using SAS PROC MIXED (ver 9.3, SAS Institute, Cary, NC) with baseline values for these measures used as covariates. Comparisons will be made for data obtained for the 12 week treatment period for the two conditions.

5. Demonstrate that ZON administration will reduce impulsive and risk taking behaviors. Our working hypothesis is that the ZON will decrease risk taking behavior as assessed using the Rogers Risk Task and the Balloon Analog Risk Task and impulsivity as measured using the Go/NoGo and the Continuous Performance Test (CPT).

Repeated measures mixed models analysis will be used to analyze data obtained for pre-randomization and week 12 data for the Rogers Risk Task, the Balloon Analog Risk Task, the Go/NoGoTask, the CPT, and Go/No Go. Model generated group least square means values for week 12 will be compared using student t-tests.

[name] will provide statistical consultation. He will not have access to identifiable information and will not have any contact with study participants.

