CONN creates subject-specific ROI files and registers them to the subject space. 99 ROIs will be used as the seeds of interest for whole-brain subject-specific ROI-ROI connectivity analyses.

**Power Analysis:** Power analysis for drinks consumed per day during the last three weeks of treatment were determined using data for the placebo and zonisamide groups from our previous study (Knapp et al., 2015). A power value of 0.9 was found for a group size of 40, with alpha=0.05, and with an effect size of 0.74. In our previous study of ZON approximately 20% of subjects dropped out before week 12 of the study. Consequently, we will randomize 50 subjects per group to reach a target of 40 subjects in week 12 of the present study. Based on data reported by Rubio et al. (2009) for errors of commission on the CPT, a measure of impulsivity, a power value of 0.97 would be obtained for an alpha value of 0.05 for a group size of 40. Based on the findings of Myrick et al., (2008) for the difference between the activation of the ventral striatum for placebo and naltrexone groups a power of 0.88 was seen for an effect size of 0.7 for a group size of 40.

**Safety Analysis:** For safety, subjects will be assessed as having had any serious adverse event during the treatment period or not, and additional analyses will be done by separate types of adverse events. Tolerability will be assessed as a subject being able to continue on the study drug for the entire study duration without requiring discontinuation. The safety and tolerability of the study medications will be first assessed using contingency tables and chi-square tests. Fisher's exact test will be employed for rare adverse events. The chi-square analysis will be followed by logistic regression analyses, adjusting for the stratification factor. Time to drug discontinuation for serious adverse events and time to withdrawal from the study for any reason will be assessed using Kaplan-Meier survival curves and compared between study treatments using the log rank test. Poisson regression will be used to evaluate the rate of serious adverse events by arm stratified by the time periods of dosage escalation, dosage maintenance, and dosage taper.

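### The stated 0.90 power belongs to drinks per day in the last three weeks; the Aim 4 comparison covers all 12 weeks on three measures, with no primary measure, contrast or power named

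*Combined protocol and SAP*

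**What the plan says.** **What is powered.** The Power Analysis paragraph at the end of Section L is headed by the words "Power analysis for drinks consumed per day during the last three weeks of treatment". It gives power 0.9 for 40 per group, alpha 0.05 and effect size 0.74, taken from the team's previous zonisamide study. With about 20% dropout, 50 per arm are randomised. The other two power figures in that paragraph concern CPT errors and ventral striatum activation, not drinking.

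**What is tested.** Item 4 of Data Analysis (Aim 4) plans a repeated measures mixed model with the baseline value as covariate, and says: "Comparisons will be made for data obtained for the 12 week treatment period for the two conditions". Three measures are listed: percent days drinking, drinks per day, and percent days heavy drinking. The hypothesis names two of them: "Our working hypothesis is that the drinks consumed per day and percent days drinking will be significantly lower in AUD subjects receiving ZON". None is called primary.

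**Nearby text.** Aim 5 does state its contrast: "Model generated group least square means values for week 12 will be compared using student t-tests". The Study Summary expects the zonisamide group to "have significantly greater reductions in alcohol consumption by the end of a 12-week treatment period", which fixes neither a measure nor a contrast. A late window in study weeks, "during study weeks 10 to 12", appears only in Aim 3, for a different outcome.

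**Randomisation.** "An adaptive randomization will be used, where gender, heavy drinking, handedness, and smoking status will be variable levels". The Aim 4 model does not list these factors.

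**The concern.** A power statement is useful only if it refers to the test that will be run. Here the powered quantity is a late-window mean of one measure, while the planned comparison spans 12 weeks and several measures. In the dosage table, weeks 1 to 6 of those 12 are escalation weeks, so the average effect over 12 weeks need not equal the effect in the last three. A reader cannot say which Aim 4 test is the main one or what power it has. With both the measure and the contrast open, the choice could also be made after the data are seen. This matters because the drinking calculation is the stated basis for 50 per arm and drinking is the first hypothesis in the Study Summary.

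**Working it through.** **1. Reproduce the plan's figure.** Inputs from Power Analysis: d = 0.74, n = 40 per arm, alpha = 0.05. Noncentrality = 0.74 × √(40/2) = 3.31 on 78 df. Two-sided power = 0.905 (normal approximation 0.911). One-sided power would be 0.949, so the plan's figure is two-sided. Dropout: 40/(1 − 0.20) = 50. Both stated figures hold.

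**2. Change only the window.** The documents give no weekly effects or correlations, so these are assumptions: equal weekly variances, equal correlation ρ between weeks (compound symmetry), and d = 0.74 for the mean of the last three weeks. Let f be the average effect over 12 weeks as a fraction of the late effect. Then

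d(12 weeks) = 0.74 × f × √{[ρ + (1 − ρ)/3] / [ρ + (1 − ρ)/12]}.

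If the effect follows the tabulated dose, the weekly fractions are 0.25, 0.25, 0.5, 0.5, 0.75, 0.75 and then 1 six times, so f = 9/12 = 0.75. If it appears only at the target dose, f = 6/12 = 0.50. For example, at ρ = 0.4 and f = 0.75: 0.74 × 0.75 × √(0.60/0.45) = 0.641. With 40 per arm and no baseline adjustment, against 0.905 for the late window:

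| Effect over weeks 1–12 | d, ρ = 0.4 to 0.8 | Power |
|---|---|---|
| Full from week 1 (f = 1) | 0.854 to 0.762 | 0.965 to 0.920 |
| Follows dose (f = 0.75) | 0.641 to 0.572 | 0.81 to 0.71 |
| Target dose only (f = 0.50) | 0.427 to 0.381 | 0.47 to 0.39 |

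**3. Credit baseline adjustment and partial data.** Further assumptions: 50 per arm, of whom 10 drop out with last observed week spread evenly over weeks 1 to 11; a baseline covariate correlated 0.5 with the 12-week mean; known covariance; generalised least squares; 97 df. All contrasts now come from the same data, so they compare like with like.

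| Contrast (compound symmetry, ρ = 0.4 to 0.8) | Follows dose | Target dose only |
|---|---|---|
| Last three weeks, separate effect each week | 0.97 to 0.98 | 0.97 to 0.98 |
| 12-week average, separate effect each week | 0.95 to 0.90 | 0.67 to 0.58 |
| Single treatment effect over 12 weeks | 0.93 to 0.86 | 0.57 to 0.47 |

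The last two rows differ because one model lets the treatment effect vary by week and the other does not. Aim 4 does not say which is meant.

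**4. Change the correlation structure.** Under AR(1) with ρ = 0.5, a dose-proportional effect and otherwise the same settings, the 12-week average has power 0.999 against 0.94 for the last three weeks. The order is reversed.

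**5. Multiplicity, conditionally.** If significance on either hypothesised measure counted as success, the two-sided familywise error would be 7.0% at a correlation of 0.9 between the two test statistics and 8.3% at 0.7 (bivariate normal). If both are required it is at most 5%.

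**6. Randomisation factors.** If the four factors explain a further share R² of the variance (assumed 2% to 10%), d becomes 0.74/√(1 − R²), that is 0.748 to 0.780. On 78 − 4 = 74 df with 40 per arm, power goes from 0.905 to between 0.91 and 0.93.

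**The case against.** The Aim 4 sentence reads most naturally as a treatment effect over 12 weeks, and drinks per day is in effect the lead measure because it is the only drinking measure powered. Sizing a trial on a two-group effect and analysing it with a mixed model is common practice, and the model can yield a late-window estimate. Much of this is fair, and it is why the remedy is cheap. But on that natural reading the tested quantity is still not the powered one, and a lead measure that must be inferred has not been pre-specified. Aim 5 shows that the plan can name a contrast when it chooses to.

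Three stronger readings are tempting, and the documents support none of them:

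- *The trial is underpowered.* The weekly effects and correlations are not given. Baseline adjustment and partial data from dropouts raise power, and an early effect or rapidly decaying correlation can put the 12-week average above 0.90.
- *The 0.90 is wrong.* It reproduces; it simply belongs to a different quantity.
- *Type I error is inflated.* The hypothesis joins its two measures with 'and', which suggests that both are required. An either-measure rule is written nowhere.

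The objection also has force on the covariates. Heavy drinking may overlap the baseline drinking value already in the model, and the gain is small, so that item is an improvement rather than a defect.

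**Conclusion.** The concern holds as a mismatch between the powered and the planned comparison. The stated 0.90 applies to drinks per day in the last three weeks. No power is given for the 12-week Aim 4 comparison, and neither its primary measure nor its contrast is named. The mismatch is read directly from the text and needs no assumption.

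Its numerical size does rest on assumptions. With compound symmetry and a baseline correlation of 0.5, the 12-week average loses a little power if the effect follows dose and a great deal if it needs the target dose. Under AR(1) with ρ = 0.5 and a dose-proportional effect it gains. Size and direction are therefore undetermined by the documents. This should be fixed before analysis; it does not show that the sample size is inadequate.

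**What to change.** 1. Name drinks per day as the single primary drinking measure, with percent days drinking and percent days heavy drinking secondary. Then choose one of two routes; the choice of estimand is the trial team's:
   - make the treatment difference over the last three treatment weeks, given in study weeks, the primary contrast, from a PROC MIXED model with a treatment-by-week term, so that the stated power applies to the test; or
   - keep the 12-week comparison, say whether it is an average of weekly effects or a single treatment effect, and restate its power with the assumed weekly effects, correlation structure and baseline correlation.
2. As a low-cost improvement, add gender, heavy drinking, handedness and smoking status to the Aim 4 model. This costs about four degrees of freedom if each has two levels.
3. Separately, reconcile the treatment schedule, because it determines what the last three weeks cover. Study Sessions says "subjects will receive either ZON or drug placebo (and TC) for 12 weeks, followed by a 2 week taper off medication". The Zonisamide text gives a seven-week titration and 300 mg throughout week 12, whereas its table reaches 400 mg at week 7 and holds it through week 12. The Post-Treatment Period text calls week 14 the final week of drug treatment. No view is taken on which is right.

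The cost is SAP wording and, for the second route, a new power calculation. No additional data collection is needed.
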